#### 1.3 Study Sites

There will be 4 study sites: St. Cloud ENT, the Mayo Clinic, Children's Hospitals and Clinics of MN, and the University of Minnesota Children's Hospital. St. Cloud ENT will enroll patients prospectively. Data from the other three sites will be retrospectively procured from the previous multi-site moderate sedation study using data that was not previously submitted to FDA in support of the 510k application for use of the H-TTS in children under moderate sedation (K142282). This clinical data was procured after K142282 had already been submitted.

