## Poolability of prospective and retrospective patients:

Subjects from the previous multi-site moderate sedation study who were not included in the previous 510k (K142282) data will be included in this data analysis if they met the following criteria: children 6 months through 5 years of age, who are candidates for placement of VT and required use of the H-TTS under moderate sedation and accompanying local anesthetic.

Poolability of the subjects prospectively enrolled in the 522 study and those retrospectively procured through the multi-site conscious sedation study will be tested using Fisher's Exact test. The proportion of subjects requiring conversion will be analyzed in a 2x2 table where the rows consist of the study from which the subjects information came and the columns are whether or not the subject required conversion. If the p-value for this comparison is greater than 0.15, the data will be considered poolable for the purposes of statistical analysis.

In addition to assessing poolability of the conversion rates between sites, additional comparisons between the sites providing retrospective data and the site providing prospective data will be completed. Specifically, subject age, which is the only common demographic, will be compared between the combined data from sites supplying retrospective data and the site providing prospective data. Age data will be compared using a two sample Wilcoxon test.

An ad hoc analysis based on the outcome of any procedure that was converted will also be attempted. The outcome of converted procedures will be classified as successful or unsuccessful and the differences in successful outcomes will be compared between the sites providing retrospective data and the site providing prospective data. A Fisher's Exact Test will be used for this comparison. This analysis is done only on converted cases therefore it should be noted that the sample size for this analysis may be extremely small.

Rates will be calculated for the outcome variables and detailed summaries for all adverse events will be provided. Statistical summaries will include number, mean, standard deviation and range for continuous parameters or frequency and percent for categorical parameters. No formal statistical hypothesis tests are planned.

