Ad hoc analyses using logistic regression models will be used to assess the relationship between selected parameters and the outcome of conversion to general anesthesia. The prespecified parameters will be assessed individually in univariable models with a subset of these parameters being used in the multi-variate model. The pre-specified parameters are age, sex, weight, type of anesthesia/sedation, number of ears treated, surgeon experience, surgery duration, patient movement, anatomy and lack of visualization. After each parameter has been modelled univariately (stage 1), those parameters with a p-value less than 0.20 will be included in a multivariable model and a stepwise selection process will be employed to determine if any parameters have a statistically significant association with conversion. The nominal p-value for retention in the final reduced model will be 0.05.

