## 4.0 STUDY ENDPOINTS

4.1 The rate of conversion from moderate sedation to general anesthesia, along with surgeon experience, the patient and procedure characteristics associated with the decision to convert (age, sex, weight, type of anesthesia/sedation, number of ears treated, surgery duration (tympanostomy time for each ear), patient movement, anatomy, and lack of visualization). (Note: conversion to general anesthesia is not an adverse event, nor is it considered an additional risk to the patient.)

**4.2** The rate of intra-operative and pre-discharge AEs and rates for each specific type of event.

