#### 8.0 SURGICAL PROCEDURE

The tympanostomy procedures will take place in a hospital or ambulatory surgery center. The choice of anesthesia drugs for moderate sedation will be up to the attending physicians. The H-TTS will be used to make the myringotomy incision and place the VT. Patients will receive moderate sedation and local anesthetic. Per standard sedation procedure, a patient may be converted to general anesthesia if deemed appropriate by the surgeon.

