#### **10.0 STUDY PROCEDURES FOR PROSPECTIVE PATIENTS**

#### 10.1 Summary of Study Procedures

Documentation of patient eligibility, anesthesia conversions, procedural and immediate postoperative adverse events will be collected via electronic data capture (EDC). Investigators will sign the CRFs via electronic signatures.

CRFs	Type of Form	Timing
#1	Enrollment/Procedure	Time of surgery
#2	Adverse events	Time of surgery until discharge

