# 10.2 Enrollment/Surgical Procedure

Subjects will undergo evaluation at the time of referral or at the time of the procedure to confirm that they are candidates for VT placement using the H-TTS under moderate sedation and local anesthetic. The type of anesthesia and reason for conversion to general anesthesia, if needed, will be documented. Surgery duration will be defined for each ear as the time from when the H-TTS enters the ear until a VT is in place across the tympanic membrane.

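### Surgery duration is screened as a predictor of conversion, but its per-ear clock does not stop at conversion, so it can include time after the decision it is meant to explain.

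*Combined protocol and SAP*

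**What the plan says.** The logistic regression paragraph of section 3.3, which follows the poolability text, models conversion to general anesthesia (yes or no) on a pre-specified list that includes "number of ears treated, surgeon experience, surgery duration". Each parameter is first fitted alone. Those with p below 0.20 go into a multivariable model with stepwise selection, and 0.05 is the level for staying in.

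Section 4.1 places duration, specified by ear, among the "patient and procedure characteristics associated with the decision to convert". Section 10.2 gives the only definition of duration: for each ear, "the time from when the H-TTS enters the ear until a VT is in place across the tympanic membrane". It says that the type of anesthesia and the reason for any conversion are documented, and it does not mention the time of conversion. Under section 8.0, "a patient may be converted to general anesthesia if deemed appropriate by the surgeon", so conversion is an event of the child and not of an ear. Section 5.0 counts a child as enrolled once the incision is made and tube delivery is attempted, so at least one ear's clock has started in every enrolled child.

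The definition stands in section 10, headed "STUDY PROCEDURES FOR PROSPECTIVE PATIENTS". For the other sites, section 1.3 says: "Data from the other three sites will be retrospectively procured from the previous multi-site moderate sedation study".

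**The concern.** A predictor should be fixed before the outcome it is meant to explain. As defined, duration can keep accumulating after the surgeon has decided to convert. An association between duration and conversion could then arise because converting changed the duration, and not because a long attempt led to conversion.

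What is at stake is the explanatory half of endpoint 4.1. Duration could be reported as a factor in the decision when it is partly a result of that decision. If it also enters the multivariable model, the other estimates are adjusted for a variable that may be a consequence of the outcome.

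**Working it through.** **Step 1. Where the decision can fall relative to the clock.** Sections 5.0, 8.0 and 10.2 together allow three cases:

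- Conversion after the last tube is in place: every clock has stopped, and no time after the decision is counted.
- Conversion while an ear's clock is running: that ear's duration is partly after the decision. If a second ear follows, its duration is wholly after it.
- Conversion between ears: the first ear's duration is clean, and the second ear's is wholly after the decision.

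No section separates these cases or says how often each occurs. The definitions therefore establish that the problem can arise. They do not say how large it is, or in which direction: time spent converting lengthens an ear's duration, while an ear treated after conversion may go faster.

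**Step 2. Inputs for an illustration.** From the plan: N = 109 and an expected conversion rate of 15% (section 3.3), so 0.15 × 109 = 16.35 expected conversions and 92.65 non-conversions. Assumed, because the plan gives no figure for duration: mean 3 and SD 2 minutes (gamma), one duration per child, and no true relation between duration before the decision and conversion. Added minutes d fall in a share q of converted children.

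**Step 3. Check by hand.** The mean shift is d × q. The standard error of the difference in means is about 2 × √(1/16.35 + 1/92.65) = 2 × √0.0720 = 0.54 minutes. The chance of two-sided p<0.05 is about Φ(s − 1.96) + Φ(−s − 1.96), with s = d × q / 0.54:

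- +1 minute in a quarter: s = 0.47, about 8%.
- +1 minute in half: s = 0.93, about 15%.
- +1 minute in all: s = 1.86, about 46%.
- +2 minutes in all: s = 3.73, about 96%.

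**Step 4. Simulation.** 6,000 trials per setting, N = 109, univariable logistic regression with a Wald test:

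| Added time in converted children | p<0.20 | p<0.05 |
|---|---|---|
| none | 20.1% | 4.2% |
| +0.5 minute in a quarter | 19.7% | 5.1% |
| +1 minute in a quarter | 23.7% | 7.1% |
| +1 minute in half | 35.6% | 14.3% |
| +1 minute in all | 68.7% | 41.0% |
| +2 minutes in a quarter | 36.6% | 14.3% |
| +2 minutes in all | 99.0% | 93.5% |

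If duration is 1 minute shorter in all converted children (floor 0.1 minute), 41.4% of trials reach p<0.05, almost all in the reverse direction.

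**Step 5. Sensitivity to the assumptions.**

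- Fewer usable children: +1 minute in all gives 22.4% at N = 60 and 15.3% at N = 40.
- Another distribution: log-normal with median 3 minutes and log-SD 0.6, and an exponential delay in every converted child, gives 4.0% with no delay, 31.6% with a mean delay of 1 minute and 74.9% with 2 minutes.
- Two ears: between-ear correlation 0.5 (assumed), with +2 minutes in the second ear of every converted child, gives 51.7% using the ear mean and 69.8% using the longer ear. Using the first ear alone gives 4.0% to 4.4% in every setting. That last result holds only because no time was added to the first ear; it does not cover conversion during the first ear.

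**The case against.** The best counter-argument is that the effect may be nil. No section says when conversions happen relative to the clock. Section 1.2 describes incision and tube insertion in one pass, so a clock that runs through conversion is not shown to be typical. The minutes, their spread and the share affected are all assumed, and the large percentages need every converted child to carry added time. This stands: with half a minute or one minute in a quarter of converted children, the rate barely moves.

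The simulated test is also not the planned procedure. The p<0.20 column matches stage 1. The p<0.05 column is a univariable test, not retention after stepwise selection alongside movement, anatomy and visualization. This stands too, so the figures show direction and range and do not predict the final model.

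The plan also labels the models ad hoc, seeks only association, and states: "No formal statistical hypothesis tests are planned". This lowers the weight of the point but does not remove it. The list and both thresholds are fixed in advance, and section 4.1 ties the characteristics to the decision itself.

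Stopping the clock at conversion might look simpler. The text mentions no time of conversion; the case report forms are not in the public text, so such a field cannot be ruled out. But cutting time off only in converted children would itself shorten their durations.

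A reader might infer that dropping duration altogether is required. The documents do not support that: section 4.1 names it as something to report, and a real link between a long attempt and conversion is possible.

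**Conclusion.** The point holds as a matter of definition: following the plan as written can put time after the outcome into a predictor of that outcome. The size cannot be known from the documents. It is negligible if few conversions occur with tube work remaining and large if most do, and the direction is open. The percentages rest on assumed durations and added minutes; only 109 and 15% are the plan's.

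A reader might go further and infer that any duration finding will be false, or that it will be biased upward. Neither follows, because the documents do not say when conversions occur or whether ears treated afterwards take longer. Nor does the point reach the conversion rate, the adverse event rates or the sample size, none of which uses duration.

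The absence of a rule for combining two ears, and of a stated timing definition for the three retrospective sites, might also be read as defects. They are clarifications only. The earlier study's protocol is not among the documents, and wording could settle both.

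This is a worthwhile, low-cost improvement to a secondary analysis.

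**What to change.** In the logistic regression paragraph of section 3.3, take surgery duration out of the p<0.20 screen and the main stepwise model. Report it under endpoint 4.1 as a per-ear summary by conversion status (number, mean, standard deviation and range, which the plan already provides for continuous variables). Add a note that in converted children it may include time after the decision.

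If an estimate is wanted, add duration in one separate model, labelled as a sensitivity analysis and not interpreted as a factor in the decision to convert.

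As clarifications, state how two ears are combined if that model is fitted, and whether the retrospective durations follow the section 10.2 definition. If they do not, summarise the two cohorts separately.

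The cost is wording only, with no new data. The main model gives no odds ratio for duration and does not adjust for it, so a genuine link between a long procedure and conversion would show only in the descriptive summary or the sensitivity model.

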#### Sample size:

The sample size was chosen to ensure an adequate precision in the estimation of the conversion rate. Based on an expected conversion rate of 15%, a sample size of 109 subjects will provide an upper, one-sided, Wilson 95% confidence bound that is no more than 6% greater than the estimated conversion rate with a probability of approximately 0.80.

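### The p<0.20 logistic screen names neither its test nor a rule for separation; if Wald p-values are used, a binary parameter with an empty cell is dropped however strong it is

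*Combined protocol and SAP*

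**What the plan says.** The regression is described in section 3.3 of the combined protocol and SAP, in the last paragraph under the heading on poolability: "Ad hoc analyses using logistic regression models will be used to assess the relationship between selected parameters and the outcome of conversion" to general anesthesia. Ten parameters are listed: age, sex, weight, and then "type of anesthesia/sedation, number of ears treated, surgeon experience, surgery duration, patient movement, anatomy and lack of visualization". The selection rule is: "After each parameter has been modelled univariately (stage 1), those parameters with a p-value less than 0.20 will be included" in a multivariable model. Stepwise selection follows, with retention at 0.05.

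The text does not say whether the p-value is Wald, score or likelihood ratio. It names no exact or penalised estimator and gives no rule for sparse levels, separation or non-convergence. Fisher's exact test appears in section 3.3 only for the comparisons between prospective and retrospective data.

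Three other places bear on the point:
- The sample-size paragraph fixes the expected number of events: "Based on an expected conversion rate of 15%, a sample size of 109 subjects".
- Section 8.0 leaves the sedation regimen open: "The choice of anesthesia drugs for moderate sedation will be up to the attending physicians".
- Section 4.1 makes the characteristics associated with conversion part of the endpoint, alongside the rate itself.

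**The concern.** Logistic regression by maximum likelihood has no finite estimate for a level in which nobody, or everybody, has the event. The log odds ratio drifts outward with each iteration and its standard error grows faster, so the Wald statistic shrinks towards zero and its p-value rises towards 1. Many programs print that Wald p-value by default. A screen that reads it would record a sedation type with no conversions, or a feature present only in converted children, as unrelated to conversion.

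At stake is the list of associated characteristics in endpoint 4.1. There is also a prespecification problem. If the test is chosen only after the tables are seen, that choice alone can decide whether a parameter enters the multivariable model.

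**Working it through.** **Inputs from the plan.** N = 109, expected conversion rate 15%, ten candidate parameters, screen at 0.20, retention at 0.05.

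**The plan's own figure.** The sample-size paragraph uses an "upper, one-sided, Wilson 95% confidence bound" that is "no more than 6% greater than the estimated conversion rate with a probability of approximately 0.80". Summing the binomial(109, 0.15) probabilities, the Wilson half-width is at most 0.06 for x ≤ 19, which has probability 0.8036. So the 0.80 is reproduced when the 6 points are read as the half-width. Measured from the estimate itself, the condition holds only for x ≤ 12, with probability 0.150. That difference does not affect the present point; N and the 15% are all that is used below.

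**Events.** 0.15 × 109 = 16.35 expected conversions, or about 1.6 per parameter. The tables below fix 16 of 109.

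**How easily an empty cell arises.** With 16 of 109 converted and no association, the chance that a level of k children has no conversions is C(93,k)/C(109,k): 44% for k = 5, 19% for k = 10, 3% for k = 20. With a real effect, suppose a regimen has a 20% share and a true rate of 3% (both assumed). The chance of no conversions on it is (1 − 0.20 × 0.03)^109 = 0.994^109 = 0.52. With a true rate of 10% it is 0.98^109 = 0.11.

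**Table A (assumed): 0/20 on one level, 16/89 on the other.**
- Wald, by iteratively reweighted least squares: p = 0.49, 0.73, 0.94 and 0.99 after 6, 8, 12 and 16 iterations. All exceed 0.20, and the value depends on where the software stops.
- Likelihood ratio: 2 × {[16 ln(16/89) + 73 ln(73/89)] − [16 ln(16/109) + 93 ln(93/109)]} = 2 × (−41.924 + 45.464) = 7.08, p = 0.008.
- Score p = 0.040; Fisher p = 0.040.
- Firth: for a single binary parameter the estimate equals adding 0.5 to each cell, so OR = (0.5/20.5)/(16.5/73.5) = 0.11. Penalised likelihood-ratio p = 0.033. The Wald p from the same Firth fit is 0.137, so the penalised test matters as well as the penalised estimate.

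**Table B (assumed): 4/4 with a feature, 12/105 without.** Wald p = 0.61 to 0.99 over the same iterations; likelihood ratio 0.00005; Fisher 0.0003; Firth 0.0001.

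**Extreme case.** 16/16 against 0/93: Wald p = 0.9999, likelihood-ratio p < 0.0001.

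**Three levels, one of them 0/30.** Joint tests give:

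| Converted by level | Wald p | Likelihood-ratio p |
|---|---|---|
| 8/40, 8/39, 0/30 | 0.998 | 0.003 |
| 5/40, 11/39, 0/30 | 0.237 | 0.0008 |
| 4/40, 12/39, 0/30 | 0.090 | 0.0002 |

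The first two fail a Wald screen at 0.20 and the third passes.

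**Very small levels.** 0/5: likelihood-ratio p = 0.202, Fisher p = 1.00. 0/10: likelihood-ratio p = 0.067, Firth p = 0.236. There is little information here under any method.

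**The case against.** The best counter-argument is that the plan never says Wald. A reader might infer that the p<0.20 rule itself throws out the strongest parameter. The documents do not support that: with ordinary logistic regression and a likelihood-ratio test, Tables A and B both pass easily, and a score test also keeps them. This objection stands, and the point has to be conditional on the test.

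Several further limits also stand:
- A joint Wald test on a parameter with three or more levels can survive, and the number of sedation types is not given.
- Age, weight and surgery duration are naturally continuous. If sex is near balanced, a 50-child level with no conversions would arise by chance with probability about 0.00002. The exposed parameters are those with small levels, whose coding and frequency the document does not give.
- The 19% and 44% describe levels with no association, where dropping the parameter does no harm. They show that separation can occur, not that a real factor is lost.
- Section 10.2 records the reason for conversion. If movement, anatomy and visualization are captured mainly as such reasons (an inference, since the case report forms are not available to read), an all-converted cell is a recording artefact and a small p-value would be circular. Firth estimation does not cure that.
- The regression is labelled ad hoc, and section 3.3 says that no formal hypothesis tests are planned.

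One part of the counter-argument does not carry. Naming the likelihood-ratio test repairs the screen, but the odds ratio for a separated level remains zero or infinite, so the plan would still have no usable estimate to report. Nor does the ad hoc label make the result dispensable, because section 4.1 lists these same characteristics within the endpoint.

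**Conclusion.** The gap is real but conditional. With about 16 expected conversions, the plan leaves open both the p-value that drives the screen and the handling of separation. If Wald p-values are used, a binary parameter with a none-converted or all-converted level is dropped regardless of strength (Table A: 0.94 to 0.99 near convergence, against 0.008 to 0.040 by the other tests). If a likelihood-ratio or score test is used, a strong one is kept, but without a finite odds ratio.

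It would go too far to say that endpoint 4.1 will list the wrong characteristics. That needs a Wald screen, binary coding (or an unfavourable multi-level table) and an empty cell in a genuine predictor, and the plan establishes none of these. All level sizes above are assumed. The conversion rate, its confidence bound and the adverse-event rates are untouched. This is an inexpensive improvement to a secondary analysis.

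**What to change.** In the regression paragraph of section 3.3:
1. Fit the univariable and multivariable models by Firth penalised likelihood.
2. Base both the 0.20 screen and the 0.05 retention on penalised likelihood-ratio p-values, taken jointly over levels for a multi-level parameter. Do not use Wald p-values, including those from a Firth fit.
3. Report odds ratios with profile-likelihood 95% confidence intervals.
4. Combine sparse sedation types before outcome is examined, using a minimum group size that the sponsor sets in advance.

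At a minimum, name the likelihood-ratio test for the screen. That prevents the wrongful discard but leaves the infinite or zero odds ratio.

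The cost is SAP wording and a standard software option. Estimates shrink slightly, and p-values for very small levels are somewhat larger than from the ordinary likelihood-ratio test (0/10: 0.24 against 0.07), so a weakly supported small level may fail the screen where it would otherwise have passed.

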## 6.0 SAMPLE SIZE

This study will include a minimum of 109 treated patients.

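### Choosing among ten parameters at an unadjusted 0.05 on about 16 conversions gives a 28% to 48% chance of a false associated factor if none is real, and exaggerates modest real effects that are selected

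*Combined protocol and SAP*

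**What the plan says.** The logistic regression paragraph in section 3.3, labelled ad hoc, names ten parameters: age, weight, sex, sedation type, ears treated, surgeon experience, duration of surgery, movement, anatomy and poor visualization. Each is modelled alone. Then "those parameters with a p-value less than 0.20 will be included in a multivariable model and a stepwise selection process will be employed", with 0.05 as the nominal level for staying in the final model. The stated purpose is to establish whether any parameter is significantly associated with conversion.

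The paragraph just before it says "No formal statistical hypothesis tests are planned".

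The sample size is set for the conversion rate alone: "Based on an expected conversion rate of 15%, a sample size of 109 subjects" is justified by a Wilson bound "that is no more than 6% greater than the estimated conversion rate with a probability of approximately 0.80". Section 6.0 adds that "This study will include a minimum of 109 treated patients".

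Section 4.1 pairs the conversion rate with "the patient and procedure characteristics associated with the decision to convert" and lists the same ten items.

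The plan does not name the test (Wald or likelihood-ratio), the stepwise direction or the entry level. It gives no multiplicity allowance, shrinkage, validation or limit on model size. Section 3.3 warns that the comparison among converted cases may rest on very few subjects, but it gives no such warning for this model, which depends on the same conversions.

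**The concern.** A rule that keeps whatever passes 0.05, applied to ten candidates and few events, yields a list that is partly chance, with estimates that lean toward the extreme because they had to be extreme to be kept. The list is also more than a side product. Section 4.1 makes the associated characteristics part of an endpoint, and section 2.0 places the study under section 522 post-market surveillance. A chance finding or an exaggerated one could enter the final report as a reason why children convert. The plan also contradicts itself, since it disclaims formal tests and then uses p-values to declare significance.

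**Working it through.** **Inputs from the plan.** N = 109 (a minimum); expected conversion 15%; ten parameters; screen at 0.20; retention at 0.05.

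**The plan's own figure.** The stated probability of about 0.80 can be reproduced. With z = 1.645, the Wilson half-width about its own center is z/(1 + z²/n) × √(p(1−p)/n + z²/4n²). At n = 109 this is at most 0.06 for up to 19 conversions, and P(X ≤ 19) for a binomial with n = 109 and p = 0.15 is 0.8036. (Taken literally, as upper bound minus estimated rate, the probability is 0.15; that is a separate matter.) The size calculation therefore addresses the rate only and says nothing about a regression model.

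**Events available.** 109 × 0.15 = 16.35 conversions, with a central 90% binomial range of 10 to 23. Per parameter: 16.35 / 10 = 1.6.

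**Benchmark for false retention.** For ten independent null tests at 0.05: 1 − 0.95^10 = 40.1%.

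**Simulation of the rule.** N = 109, 15% events, ten parameters unrelated to conversion, univariable screen at 0.20, then backward or forward selection at 0.05; 2,000 studies per scenario. Covariate distributions and correlations are assumptions, because the plan gives none. The share of studies retaining at least one parameter was:

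| Covariates | Wald | Likelihood-ratio |
|---|---|---|
| Ten continuous | 37% | 42–43% |
| Three continuous, seven binary | 31–33% | 46–48% |
| As above, balanced binaries | 34–35% | 42–43% |
| As above, rare binaries | 28–29% | 35–36% |

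A repeat simulation gave 34% (Wald) and 45% (likelihood-ratio), inside these ranges.

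**What drives it.** The share of studies with any univariable p below 0.05 lies within about 1.5 points of each figure, so the 0.20 screen adds almost nothing. Testing each parameter at 0.05/10 brought the share down to 5.0% (likelihood-ratio) or 2.4% (Wald), which again points to the ten looks.

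**Exaggeration of a real effect.** One real parameter and nine nulls:

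| True odds ratio per SD | Selected in | Median reported when selected | Mean log odds ratio relative to truth |
|---|---|---|---|
| 1.5 | 26–34% | about 2.1 | 1.9–2.0 times |
| 2.0 | 56–70% | about 2.4 | 1.3–1.4 times |
| 2.5 | 74–88% | 2.8–2.9 | about 1.2 times |

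The repeat simulation gave 2.1 for a true 1.5 and 2.7 for a true 2.5. Without selection, the univariable estimate for a true 1.5 had a median of 1.52, so the distortion comes from selecting and not from the univariable fit.

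**The case against.** The strongest defense is that the plan calls this work ad hoc, describes 0.05 as nominal and never claims a 5% error rate across the ten parameters. Section 4.1 does not require a selected model, and descriptive summaries could serve it. This lowers the weight of the point but does not remove it: the paragraph still sets out to declare significance, on items that section 4.1 lists in an endpoint.

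A second objection is that ten null parameters is an unlikely state of affairs. Movement, anatomy and poor visualization may be reasons for converting, and section 10.2 has the reason recorded. That is fair. With one real effect and nine nulls, the chance of a false retained parameter was still 33% to 46%. If only six parameters were null, the benchmark would be 1 − 0.95^6 = 26%.

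A reader might also infer three things that the documents do not support:
- That nearly half of such studies would name a false factor. That is the top of the range, reached with likelihood-ratio tests and mixed covariates, and the plan does not name its test.
- That testing in two stages is the cause. The screen barely changes the result.
- That odds ratios appear only for parameters that were kept. The paragraph sets a rule for staying in the final model; it does not say that the univariable results are withheld.

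**Conclusion.** The point holds as a weakness of the analysis plan. On about 16 conversions, the rule has roughly a 28% to 48% chance of retaining at least one parameter when none is related to conversion, against the 5% that a reader might take from the nominal level. The range reflects the unnamed test and the assumed covariates.

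Exaggeration is conditional on selection and depends on strength: about twofold on the log-odds scale for a true odds ratio of 1.5 per SD, and about 1.2-fold for 2.5. It would be wrong to infer that every real effect is badly inflated.

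The data may be thinner than 109 suggests. Section 3.3 says that age is the sole demographic shared by the two data sources, so sex and weight may be missing for some subjects; the split between sources is not given. With complete covariates on only 80 subjects, false retention was 29% (Wald) or 46% (likelihood-ratio); on 50, it was 24% or 45%.

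The estimates of the conversion and adverse event rates are unaffected.

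**What to change.** - Remove the selection by p-value (both the 0.20 screen and the stepwise step) and the wording about statistical significance. This also removes the conflict with the statement that no formal tests are planned.
- Report the univariable odds ratio with its 95% confidence interval for all ten parameters, whatever the p-value, labelled exploratory. Give the number of subjects and conversions behind each estimate.
- State beside the table that ten parameters were examined on about 16 events and that some intervals will exclude 1 by chance.
- If an adjusted model is wanted, specify it now with about two parameters known before the procedure and available in both data sources, preferably with Firth penalization. Age qualifies on the plan's own account; any second parameter needs its availability confirmed.

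The cost is SAP wording only, with no new data or subjects. The downside is that the report can no longer name a list of significant predictors. The change cures the selection bias and the unsupported significance claim. It does not abolish the ten looks: unadjusted intervals will exclude 1 by chance about as often as before, which is why the accompanying statement is needed.
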